ANC < 1500/mm ³	J21*	No dose modification + G-CSF

Protocole NEXT-REGIRI -Version 6.0 du 09/11/2023

Page **44** sur **86**

and Platelets > 100 000/mm ³		
Platelets < 100 000/mm ³	121*	Padusa by 1 dosa laval
Whatever the number of ANC	JZ I"	Reduce by 1 dose level

^{*} or until 28th day as needed (maximum)

Modalities of Reintroduction of treatment : ANC \geq 1500/mm³ and Platelets \geq 100 000/mm³ If the Platelets and/or ANC values are not correct at D28, the patient will discontinue permanently the study treatment.

At the time of Nadir

In the case of a grade 4 neutropenia, whatever the duration or complication i.e by an infection or fever > 38°5, the G-CSF will be administered at the next course of treatment. If the same toxicity continues with G-CSF then the irinotecan dose will be reduced at the dose immediately inferior. If there is a third occurrence of this toxicity, the patient will permanently discontinue the study treatment.

Table 5: Action and dose modification during the administration of Regorafenib in case of hematological toxicity

Hematological toxicity (Modification dose/delay for Regorafenib)			
Grade	Treatment delay	Dose modification	
Grade 0-2	No delay in Regorafenib	No modification dose	
Grade 0-2	treatment	No modification dose	
Grade 3	No delay in Regorafenib	Reduce by 1 dose levelbc	
Grade 3	treatment	heduce by Tuose level	
	Interrupt Regorafenib		
Grade 4	until hematologic	Reduce by 1 dose level ^{bc}	
	toxicity resolves to	heduce by Tuose level	
	Grade ≤ 2ª		

a If no recovery within 30 days, the treatment will be permanently discontinued.

- b If more than 2 dose reductions are necessary, the treatment will be permanently discontinued.
- c Cf table a.

Table 6: Action and dose modification during the administration of Regorafenib in case of non-hematologic toxicity

Non-hematological toxicity (dose modification/delay for Regorafenib) (except hand-foot skin reaction, hypertension, liver function test abnormalities and diarrhea)^a

Grade	Treatment delay	Dose modification
Grade 0-2	No delay in Regorafenib treatment	No dose modification
Grade 3	Interrupt Regorafenib until non hematologic toxicity resolves to Grade ≤ 2 ^b	Reduce by 1 dose level ^{cd}
Grade 4	Discontinue treatment permanently	Discontinue treatment permanently

- a In the absence of nausea/vomiting prophylaxis and diarrhea not treated.
- b If more than 2 dose reductions are necessary, the treatment will be permanently discontinued.

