- c If no recovery within 30 days, the treatment will be permanently discontinued.
- d Cf table a.

Table 7: Delay and dose modification during the administration of Regorafenib in case of hand-foot skin reaction

Skin Toxicity Grade	Occurrence	Suggested Dose Modification
Grade 1: Numbness,	Any	Maintain dose level and institute immediately
dysesthesia, paraesthesia,		supportive measures for symptomatic relief
tingling, painless swelling,		
erythema or discomfort of		
the hands or feet which		
does not		
disrupt the patient's normal		
activities		

Protocole NEXT-REGIRI -Version 6.0 du 09/11/2023

Page 46 sur 86

Grade 2: Painful erythema	1st	Decreasing dose by one dose level ^a and
and swelling of the hands or	occurrence	institute immediately supportive measures.
feet and/or discomfort		If no improvement , interrupt therapy for a
which affects the patient's		minimum of 7 days, until toxicity resolves to
normal activities		Grade 0-1 ^{b.}
	No	Interrupt Regorafenib until toxicity resolves to
	improvement	Grade 0-1. When resuming treatment, treat at
	within 7 days	reduced dose levelab
	or	
	2nd	
	occurrence	
	3rd	Interrupt Regorafenib until toxicity resolves to
	occurrence	Grade 0-1. When resuming treatment, decrease
		dose by one additional dose levela b c
	4th	Discontinue treatment permanently
	occurrence	
Grade 3: Moist	1st	Institute supportive measures immediately.
desquamation,	occurrence	Interrupt therapy for a minimum of 7 days until
ulceration, blistering or		toxicity resolves to Grade 0-1. When resuming
severe pain of the hands or		treatment, decrease dose by one dose levelab
feet, or severe discomfort	2nd	Institute supportive measures immediately.
that causes the patient to	occurrence	Interrupt therapy for a minimum of 7 days until
be unable to work or		toxicity resolves to Grade 0-1. When resuming
perform activities of daily		treatment, decrease dose by one dose level ^{a b c}
living.	3rd	Discontinue treatment permanently
	occurrence	
a Cf table a		
1 16 1 16 1 16	. 4 (1)	

b If toxicity returns to Grade 0-1 after dose reduction, dose re-escalation is permitted at the discretion of the investigator

c Subjects requiring > 2 dose reductions should discontinue treatment

Suggestions:

Control of calluses

Before initiating treatment with regorafenib:

Protocole NEXT-REGIRI -Version 6.0 du 09/11/2023

Page **47** sur **86**

Réf interne ICM : ICM-ENR-432 Version : 001 Date d'application : 24/05/2017

- Check condition of hands and feet

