- Suggest a manicure/pedicure, when indicated
- Recommend pumice stone use for callus or 'rough spot' removal.

During regorafenib treatment:

- Avoid pressure points
- Avoid items that rub, pinch or create friction

Use of creams

Apply non-urea based creams liberally, e.g.,

- Cetaphil
- Aveeno
- Norwegian Formula
- Eucerin

Keratolytic Creams: Use sparingly and only to affected (hyperkeratotic) areas

- Urea-based creams
- Salicylic acid 6%

Alpha Hydroxy Acids (AHA) based creams

- Approximately 5-8% provide gentle chemical exfoliation
- Apply liberally two times each day

Topical analgesics like lidocaine 2% to be considered for pain control (114)

Topical corticosteroids should be considered for subjects with Grade 2 or 3 hand-foot skin reaction (114). Avoid systemic steroids.

Cushions

Protect tender areas

Use socks/gloves to cover moisturizing creams

- Wear well-padded footwear
- Use insole cushions or inserts (e.g., silicon, gel)
- Foot soaks with tepid water and Epsom salts

Table 8: Management of treatment-emergent hypertension

NCI-CTCAE V. 5.0 grade	Definition	Antihypertensive therapy	Regorafenib dosing
1	Prehypertension (systolic BP 120 - 139 mmHg or diastolic BP 80 - 89 mmHg)	None	Continue regorafenib Consider increased BP monitoring
2	Systolic BP 140 - 159 mmHg or diastolic BP 90 - 99 mmHg, OR Symptomatic increase by > 20 mmHg (diastolic) if previously within normal limits	Treat with the aim to achieve diastolic BP ≤ 90 mmHg: - If BP previously within normal limits, start antihypertensive monotherapy. - If subject already on antihypertensive medication, titrate up the dose.	If symptomatic, hold regorafenib until symptoms resolve AND diastolic BP ≤ 90 mmHg. ^a When regorafenib is restarted, continue at the same dose level.

3	Systolic BP ≥ 160 mmHg or diastolic BP ≥ 100 mmHg OR More than one drug or more intensive therapy than previously used indicated	Treat with the aim to achieve diastolic BP ≤ 90 mmHg: - Start antihypertensive medication AND/OR - Increase current	Hold regorafenib until diastolic BP ≤ 90 mm Hg, and if symptomatic, until symptoms resolve. ^a When regorafenib is restarted, continue at the same dose level. If BP is not controlled with the addition of new or more intensive therapy,
		antihypertensive medication AND/OR - Add additional antihypertensive medications.	reduce by 1 dose level.bd If Grade 3 hypertension recurs despite dose reduction and antihypertensive therapy, reduce another dose level.cd

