4	Life-threatening consequences (e.g, malignant hypertension, transient or permanent neurologic deficit, hypertensive crisis		Discontinue therapy

BP = blood pressure; NCI-CTCAE=National Cancer Institute-common terminology criteria for adverse events a Subjects requiring a delay of study treatment > 4 weeks should go off regorafenib.

Blood Pressure should be monitored weekly for the first 6 weeks of treatment. The blood pressure will be recorded by the treating physician and entered onto the e-CRF.

Any blood pressure that is out of normal range must be reported to the treating physician. Blood pressure measurements considered out of normal range are diastolic ≥100 mmHg and systolic ≥150 mmHg, or a ≥20 mmHg increase in diastolic measurement if the measurement was previously within normal limits.

b If BP remains controlled for at least one full cycle, dose re-escalation is permitted at the investigator's discretion.

c Subjects requiring > 2 dose level reductions (< 80 mg reduction) should go off regorafenib therapy.

d Cf table a.

The dose modification schedule for treatment emergent hypertension during regorafenib dosing should be followed (see [Table 11]). Subjects' blood pressure (BP) measurements will be monitored and appropriate treatment to effectively control hypertension under regorafenib treatment is strongly recommended.

The selection of anti-hypertensive medication used in this setting should be performed at the investigator's discretion, considering possible site-specific treatment guidelines. All medication should be recorded in the subjects e-CRF.

Table 9: Drug-related liver function test abnormalities

Elevations of	Occurence	Management
alanine aminotransférase (ALT)		
and/or aspartate aminotransférase (AST)		
≤ 5 times upper limit of normal (ULN) (Grade	Any	Continue treatment by
2)	occurence	Regorafenib. Control liver
		function every week until ALT
		and AST values return to < 3
		times ULN (grade 1)
		orbaseline .
> 5 times ULN AND ≤ 20 times ULN (Grade 3)	1 st occurence	Interrupt Regorafenib.
		Control ALT and AST
		values every week until
		they return to < 3 times
		ULN or baseline.
		Resuming treatment: if the
		potential benefit outweighs
		the risk of hepatic toxicity,
		reintroduce Regorafenib
		and reduce the dose of
		one tablet (40 mg) and
		control liver function every
		week for at least 4 weeks.
	2 nd	Discontinue regorafenib

Protocole NEXT-REGIRI -Version 6.0 du 09/11/2023

Page **51** sur **86**

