4	Life-threatening consequences (e.g, malignant hypertension, transient or permanent neurologic deficit, hypertensive crisis		Discontinue therapy

BP = blood pressure; NCI-CTCAE=National Cancer Institute-common terminology criteria for adverse events a Subjects requiring a delay of study treatment > 4 weeks should go off regorafenib.

Blood Pressure should be monitored weekly for the first 6 weeks of treatment. The blood pressure will be recorded by the treating physician and entered onto the e-CRF.

Any blood pressure that is out of normal range must be reported to the treating physician. Blood pressure measurements considered out of normal range are diastolic \geq 100 mmHg and systolic \geq 150 mmHg, or a \geq 20 mmHg increase in diastolic measurement if the measurement was previously within normal limits.

b If BP remains controlled for at least one full cycle, dose re-escalation is permitted at the investigator's discretion.

c Subjects requiring > 2 dose level reductions (< 80 mg reduction) should go off regorafenib therapy.

d Cf table a.

The dose modification schedule for treatment emergent hypertension during regorafenib dosing should be followed (see [Table 12]). Subjects' blood pressure (BP) measurements will be monitored and appropriate treatment to effectively control hypertension under regorafenib treatment is strongly recommended.

The selection of anti-hypertensive medication used in this setting should be performed at the investigator's discretion, considering possible site-specific treatment guidelines. All medication should be recorded in the subjects e-CRF.

Table 13: Drug-related liver dysfunction

Elevations of	Occurence	Management
alanine aminotransférase (ALT)		
and/or aspartate aminotransférase (AST)		
≤ 5 times upper limit of normal (ULN) (Grade	Any	Continue treatment by
2)	occurence	Regorafenib. Control liver
		function every week until ALT
		and AST values resolve to < 3
		times ULN (grade 1) or to
		their initial value.
> 5 times ULN AND ≤ 20 times ULN (Grade 3)	1st occurence	Interrupt Regorafenib.
		Control ALT and AST
		values every week until
		they resolve to < 3 times
		ULN or their initial value.
		Resuming treatment: if the
		benefice is superior to the
		risk of hepatic toxicity,
		reintroduce Regorafenib
		and reduce the dose of
		one tablet (40 mg) and
		control liver function every
		week for at least 4 weeks.
	2 nd	Discontinue regorafenib
	occurence	permanently

> 20 times ULN (Grade 4)	Any	Discontinue regorafenib

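### Tables 8 and 12, grade 3 row: systolic pressure alone can start a regorafenib hold, but no systolic condition is needed to end it

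*Combined protocol and SAP*

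**What the plan says.** Section 6.3 manages treatment-emergent hypertension in Table 8 for REGIRI (arm A) and Table 12 for regorafenib alone (arm B). The grade 3 rows match on every element used here.

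- **Entry by pressure:** "Systolic BP ≥ 160 mmHg or diastolic BP ≥ 100 mmHg". Either component is enough. The row can also be entered when more than one drug, or more intensive therapy than before, is indicated.
- **Treatment aim:** "Treat with the aim to achieve diastolic BP ≤ 90 mmHg". No systolic aim is given.
- **Release from the hold:** "Hold regorafenib until diastolic BP ≤ 90 mm Hg, and if symptomatic, until symptoms resolve".
- **Dose at restart:** "When regorafenib is restarted, continue at the same dose level. If BP is not controlled with the addition of new or more intensive therapy", in which case the dose drops one level. If grade 3 hypertension recurs despite this, it drops another level.
- **Limits:** footnote a stops regorafenib after a delay of more than 4 weeks, and footnote c stops it when more than 2 reductions would be needed.

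**The concern.** A hold should end when the condition that caused it has eased. Here systolic pressure can start the hold but plays no part in ending it. For an asymptomatic patient whose only abnormal component is systolic, the hold has no effect as written. For a patient held with both components raised, regorafenib may resume once diastolic pressure falls, even if systolic is still in the grade 3 range.

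What is at stake is patient safety and uniform dosing. In an open, multicenter trial, two sites could see the same reading, one keeping regorafenib on hold and the other restarting it, and both would be following the table. The gap concerns when regorafenib resumes; the row does direct that the hypertension be treated.

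**Working it through.** There is no plan figure to reproduce, because this is a dosing rule. The check applies the entry and release conditions to the same readings.

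**Inputs** (Tables 8 and 12, grade 3 row):
- Grade 3 by pressure: S ≥ 160 or D ≥ 100.
- Current release, asymptomatic patient: D ≤ 90.
- Proposed release, asymptomatic patient: D ≤ 90 and S < 160.

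| Reading (S/D) | Grade by pressure | Current release met? | Proposed release met? |
|---|---|---|---|
| 170/85 | 3 (systolic) | yes | no |
| 170/95 | 3 (systolic) | no | no |
| 165/88 | 3 (systolic) | yes | no |
| 160/90 | 3 (systolic) | yes | no |
| 155/102 | 3 (diastolic) | no | no |
| 159/90 | 2 | yes | yes |

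On a whole-number grid (S from 100 to 219, D from 50 to 129), the pairs that are grade 3 by pressure and also releasable are those with S from 160 to 219 (60 values) and D from 50 to 90 (41 values): 60 × 41 = 2460. Under the proposed rule there are 0. This tests the logic only and says nothing about how often such readings occur.

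**Does another provision fill the gap?**
- Table 6 (arm A) and Table 10 (arm B) carry the general toxicity rules, but both exclude hypertension in their titles.
- The dose-reduction step sets the dose at restart and does not decide whether restart is allowed. Section 6.3 does not define control. If the meaning in non-inclusion criterion 10 is carried over (systolic above 140 is uncontrolled), then 165 > 140, and a patient at 165/88 on added therapy restarts at 160 − 40 = 120 mg. Restart is still not barred.
- The further reduction on recurrence and footnote c act after regorafenib has been restarted.
- Section 5.3 has the patient contact the physician at systolic 150 or above. That prompts a review but sets no restart condition.
- The arm A rule for other toxicities delays irinotecan until grade 1 or lower. If hypertension counts under it, it still governs irinotecan only, and arm B has no counterpart.
- Section 8.1 lets the investigator stop treatment. It is discretionary and sets no restart threshold.

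**Comparison with the other tables that hold regorafenib at grade 3:**
- Table 6: "Interrupt Regorafenib until non hematologic toxicity resolves to Grade ≤ 2".
- Tables 7 and 11 (hand-foot skin reaction): "toxicity resolves to Grade 0-1. When resuming".
- Table 10: delay until below grade 2.
- Tables 9 and 13 (ALT/AST): "they return to < 3 times" and "they resolve to < 3 times" the upper limit of normal, or the baseline value. Inclusion criterion 9 caps baseline at 5 × ULN, and the grade 3 row starts above 5 × ULN, so either option is below grade 3.

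All six release below grade 3. The two hypertension tables do not ensure this.

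**The case against.** The strongest reply has four parts.

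**The wording permits restart and does not compel it.** This stands. A reader might infer that the protocol instructs sites to give regorafenib at a grade 3 pressure. The documents do not support that: the release condition is a minimum, a patient at 165/88 still meets the grade 3 definition, and Section 8.1 leaves room for judgment. The row also escalates through treatment, reduction, second reduction and stopping, and the text under both tables strongly recommends effective control. These points narrow the harm, but they do not supply a systolic condition.

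**Regorafenib continues through grade 3 events elsewhere.** This also stands. Table 5 does not delay regorafenib for grade 3 hematological toxicity, and Tables 1 to 3 interrupt only irinotecan for grade 3 diarrhea. A reader might infer from the six-table comparison that Tables 8 and 12 break a protocol-wide rule. They do not. The comparison shows only that, where regorafenib is held at grade 3, the other tables release it below grade 3.

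**The diastolic criterion may be deliberate.** It appears in the treatment-aim and release columns, for grades 2 and 3, in both tables. Its source cannot be checked from these documents. Even a deliberate diastolic target leaves a hold that can be triggered and released by the same reading, and no reason for that is given.

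**A systolic release condition does not cover the third entry route.** Correct. An asymptomatic patient at 150/88 who needs a second drug is grade 3 by that route and meets both the current and the proposed release condition at once.

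**Conclusion.** The concern holds for the two pressure triggers. In both tables, an asymptomatic grade 3 reading with systolic at or above 160 and diastolic at or below 90 meets the release condition immediately, and a held patient can become eligible to restart at such a reading. The conclusion rests on a literal reading of the row and on hypertension being excluded from Tables 6 and 10, which their titles state.

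The rule applies to all 78 planned patients (2 × 39). The number who would have such a reading cannot be estimated, because the documents give no split between systolic and diastolic elevation. A reader might infer that hypertension goes unmanaged or that the survival comparison is compromised. Neither follows: antihypertensive treatment is directed at grade 3, and nothing here bears on sample size or the overall survival analysis. This is a minor patient-safety correction worth making at the next amendment.

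**What to change.** In the grade 3 row of Tables 8 and 12, add a second pressure condition to the release rule: diastolic at or below 90 mmHg AND systolic below 160 mmHg. Keep the symptom condition as it is. The value 160 is the row's own entry threshold, so no new clinical cut-off is introduced.

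Do not add systolic below 160 as a treatment aim. The grade 2 row already starts or increases therapy at systolic 140 to 159, and criterion 10 treats systolic above 140 as uncontrolled, so 159 should not appear as an acceptable target. Whether to state a systolic aim, set a stricter release limit, change the grade 2 row or add a release rule for grade 3 entered through more intensive therapy is for the clinicians to decide.

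The cost is one row of wording in two tables. Some holds will last longer, and a few more patients may pass the 4-week delay limit in footnote a and come off regorafenib.

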 of proteinuria on a 24-hour urine collection must be done.
- EORTC QLQ-C30 (appendix 2) questionnaires will be completed by the patient on Day 1 of Cycle 1 (baseline) then on the first day of every other cycle (every 8 weeks)
- Drug dispensing
- Drug accountability (pharmacy). To have complete control over the distribution and use of the study drug, the drug accountability must be performed on Day 1 for arm A (REGIRI) and B (Regorafenib) of each cycle

Provide patient's diary on C1D1. It will allow to patient to write down his oral intakes and blood pressure values

The blood pressure must be monitored weekly for the first six weeks of study treatment. The blood pressure will be recorded by the patient and entered onto his treatment diary. In the latter case, the patient should be instructed to contact the physician in the event of systolic \geq 150 mm Hg and / or diastolic \geq 100 mm Hg. The physician should confirm the reading before recording it into the e-CRF. Blood pressure measurements will be performed in patients sitting for 5 minutes prior to the evaluation. The patient should be instructed to take their blood pressure in the morning and repeat two more times for accuracy.

The following assessments should be performed on day 8 of cycle 1 and 2:

REGIRI (arm A)

- Vital signs (Heart rate and blood pressure)
- these laboratory evaluations are required: Aspartate Amino-Transferase (AST), Alanine Amino-Transferase (ALT), bilirubin (total and direct)

Stivarga® (Regorafenib) (arm B):

• Phone call by a treatment nurse for knowing if there are any adverse events and blood pressure value (current state of the art)

The following assessments should be performed on day 15 of cycle 1 and 2:

REGIRI (arm A)

- Physical examination with weight and vital signs (heart rate, blood pressure)
- ECOG performance status
- Concomitant medications (including start/stop dates, dose, indication)
- Adverse events documentation (including Start/Stop dates, seriousness, CTC notation and grading, relationship to study drug, outcome and action taken) using CTCAE V5.0
- A CBC with differential should be performed: RBC, hemoglobin, hematocrit, platelet count and WBC. WBC must include differential neutrophil, lymphocyte, monocyte, basophil and eosinophil counts
- Coagulation panel: Prothrombin time (PT) or the International Ratio of PT (PT-INR) and Partial Thromboplastin Time (PTT)
- Electrolyte panel: sodium, potassium, chloride, calcium

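### Section 6.3 joins its two blood-pressure report limits with *and* where section 5.3 has *and/or*; read literally, some grade 3 readings that call for a regorafenib hold need not be reported

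*Combined protocol and SAP*

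**What the plan says.** The text after Table 8 (arm A) in section 6.3 makes it mandatory to report out-of-range pressures to the treating physician. It defines them so: "Blood pressure measurements considered out of normal range are diastolic ≥100 mmHg and systolic ≥150 mmHg". A third trigger, joined by *or*, covers a diastolic that has climbed by 20 mmHg or more from a normal level. The same definition follows Table 12 for arm B, beginning "Blood pressure measurements considered out of normal range are diastolic". The paragraph also says who records the pressures: "The blood pressure will be recorded by the treating physician and entered onto the e-CRF".

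Section 5.3 tells patients when to contact the physician. The limits are the same, systolic ≥150 and diastolic ≥100, but the connective differs: "150 mm Hg and / or diastolic".

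The grade 3 row of Tables 8 and 12 treats either component alone as sufficient: "Systolic BP ≥ 160 mmHg or diastolic BP ≥ 100 mmHg". The action is "Hold regorafenib until diastolic BP ≤ 90 mm Hg, and if symptomatic, until symptoms resolve".

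**The concern.** The protocol sets two rules on the same pair of numbers. Under 5.3, either limit alone triggers contact. Under 6.3 as worded, both must be exceeded together, unless the diastolic has risen by at least 20 mmHg from a normal value. The grade tables side with 5.3, since one raised component is enough for grade 3 and a hold.

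The 6.3 sentence is a working safety instruction in both arms. A member of staff who applies it literally would use a narrower rule than the one the patient has been given, and need not pass on some readings for which the tables call for regorafenib to be held. What is at stake is timely dose interruption for hypertension. No under-counting of hypertension is claimed, and neither the survival comparison nor the sample size is involved.

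**Working it through.** The plan gives no figure to reproduce; this is a check of logic.

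**Notation.** s = systolic, d = diastolic, b = prior diastolic, all in mmHg.

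**Rules**
- 6.3 as written: (d ≥ 100 and s ≥ 150) or d − b ≥ 20, the last part only if b was normal.
- 5.3: s ≥ 150 or d ≥ 100.
- Grade 3 by value (Tables 8 and 12): s ≥ 160 or d ≥ 100.
- Hold still in force in a patient without symptoms: grade 3 by value and d > 90, because the hold ends at d ≤ 90.

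**Assumption.** The documents give no patient's prior diastolic, so b is varied from 60 to 90. The upper end is the eligibility limit: criterion 10 of section 4.3 excludes diastolic above 90 (or systolic above 140) despite optimal management. The rise trigger is first taken to apply at every b in this range, which is the reading most favourable to 6.3.

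**Which grade 3 readings with d > 90 escape 6.3?**

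1. *s ≥ 160.* The joint limit fails only if d ≤ 99, and the rise trigger fails only if d ≤ b + 19. Escapes are 91 ≤ d ≤ min(99, b + 19).
2. *s from 150 to 159.* Grade 3 then needs d ≥ 100, which meets the joint limit. There are no escapes.
3. *s < 150.* Grade 3 needs d ≥ 100, the joint limit fails, and the rise trigger fails if d ≤ b + 19. Escapes are 100 ≤ d ≤ b + 19.

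| Prior diastolic b | Escaping d, s ≥ 160 | Escaping d, s < 150 |
|---|---|---|
| ≤71 | none | none |
| 72 | 91 | none |
| 75 | 91–94 | none |
| 80 | 91–99 | none |
| 81 | 91–99 | 100 |
| 85 | 91–99 | 100–104 |
| 88 | 91–99 | 100–107 |
| 90 | 91–99 | 100–109 |

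**Two worked readings**
- 165/95 with b = 80: d < 100, so the joint limit is not met; the rise is 95 − 80 = 15 < 20. Not reportable under 6.3, but grade 3 (s ≥ 160) and d > 90. Rule 5.3 catches it (s ≥ 150).
- 140/102 with b = 88: s < 150, so the joint limit is not met; the rise is 102 − 88 = 14 < 20. Not reportable under 6.3, but grade 3 (d ≥ 100) and d > 90. Rule 5.3 catches it (d ≥ 100).

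The rise trigger does rescue some readings: 145/102 from b = 80 is a rise of 22 and is reportable. The gap is therefore partial.

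**Cross-check by counting.** Take whole-number grids of s 120–200, d 70–120 and b 60–89.
- Grade 3 with d > 90: (21 × 81 + 9 × 41) × 30 = 2,070 × 30 = 62,100 combinations.
- Missed by 6.3 with s ≥ 160: (1 + 2 + … + 8 + 10 × 9) × 41 = 126 × 41 = 5,166.
- Missed by 6.3 with s < 150: (1 + 2 + … + 9) × 30 = 45 × 30 = 1,350.
- Total missed: 5,166 + 1,350 = 6,516.

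These are grid cells and say nothing about how often such readings occur in patients.

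**After the change.** If s ≥ 160 or d ≥ 100, then s ≥ 150 or d ≥ 100. So the 5.3 rule, and 6.3 with *and/or*, miss no reading that is grade 3 by value, whatever b is.

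**If the prior value is not normal.** The protocol does not define normal limits here, and Tables 8 and 12 class diastolic 80–89 as prehypertension. Where the rise trigger does not apply, the escapes widen to d 91–99 with s ≥ 160 and any d ≥ 100 with s < 150. The table above is the smaller case.

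**The case against.** The best reply is that the sentence can be read as a list, with one limit for diastolic and one for systolic, either of which is out of range. Section 5.3 suggests that this was the intent, and a joint rule gives odd results: 200/95 from a prior 80 would not be reportable. That reading is possible, but the wording does not compel it. The same sentence uses *or* for its third trigger, so a literal reader has grounds to take *and* as joint. A mandatory report rule should not need another section to settle its meaning.

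A second reply is that no reading is shown to be lost. Patients contact the physician under 5.3; the physician records the pressures; there are visits, and nurse calls in cycles 1 and 2 ("Phone call by a treatment nurse for knowing if there are any adverse events and blood pressure value"). The hold itself follows Tables 8 and 12, which are clear. All of this stands and is why severity is low. It does not remove the conflict. The 5.3 route depends on the patient making contact, and the nurse calls are a point where staff could apply 6.3. The arm A paragraph also directs the reader to Table 11 for hypertension dosing, which in this version covers hand-foot skin reaction.

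A third reply is that symptomatic grade 2 hypertension also calls for a hold, and a symptomatic 145/95 with a rise below 20 escapes 5.3 and the corrected wording as well. That is correct. The claim of no misses is limited to readings that are grade 3 by value.

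**Conclusion.** The concern holds, at low severity. As written, the 6.3 report rule in both arms conflicts with the 5.3 patient instruction and omits some grade 3 readings whose diastolic is still above the level at which the hold ends. Even with the rise trigger applied throughout, escapes begin at a prior diastolic of 72 (systolic ≥160) and 81 (systolic <150). At a prior diastolic of 90 they reach 91–99 and 100–109 respectively.

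This rests on a literal reading of *and* and on assumed prior diastolic values, since the documents supply none. It is a drafting inconsistency in a safety instruction, largely covered by the protocol's other routes. It has no bearing on design, sample size or analysis.

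**What to change.** In the two 6.3 paragraphs (after Table 8 and after Table 12), replace *and* with *and/or* between the diastolic ≥100 mmHg and systolic ≥150 mmHg limits. Keep the 20 mmHg diastolic-rise trigger as it is, and leave the 5.3 patient instruction unchanged.

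The cost is one connective in two sentences. The diary, recording route, visits, design, sample size and analysis do not change.
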